2 INTRODUCTION

Triptorelin is an agonist analogue of natural GnRH. The principal modification consists of substitution of natural glycine in position 6 by a D-amino acid (D tryptophan). Clinical and animal studies have provided positive results of triptorelin's action in hormone-dependent disorders such as prostate cancer, endometriosis, central precocious puberty, uterine fibromyomas, in vitro fertilisation and breast cancer.

2.1 Study Rationale

Results from a global phase III study have shown that the new triptorelin 6-month formulation (22.5 mg) was well tolerated and rapidly induced and maintained castration in participants with locally advanced or metastatic prostate cancer [Lundstrom 2009].

The advantage of the sustained-release 6-month triptorelin pamoate formulation is that the reduced frequency of injections will provide greater convenience to both the patient and the physician and may also improve patient acceptability and compliance with the injection schedule.

The present study will assess the efficacy and safety of the sustained-release 6-month triptorelin pamoate formulation in Chinese participants with locally advanced or metastatic prostate cancer for confirming the registration of this product in China. In addition, triptorelin pharmacokinetics (PK) and testosterone pharmacodynamics (PD) will be assessed in the study population.

2.2 Background

Prostate cancer is one of the most commonly occurring malignancies in the male population and thus the second cause of death from cancer in men over 50 in the western world. In most patients, it is an androgen-dependent tumour at initial presentation.

Growth of the prostatic tissue is regulated by a network of hormones in which androgens play a major role. Gonadotropin-releasing hormone (GnRH), also known as luteinizing hormone releasing hormone (LHRH), released in a pulsatile manner by the hypothalamus, stimulates the pituitary to release in pulses the gonadotropins luteinizing hormone (LH) and follicle stimulating hormone (FSH). LH stimulates the production of testicular testosterone; however, approximately 5% of circulating testosterone is independently produced by the adrenal glands. FSH plays a role in the regulation of spermatogenesis.

Since the pioneering studies of Huggins and Hodges [1941, 1941a] in the 1940's about the regulatory role played by the testicular androgens in the growth of prostate cancer cells, the mainstay of treatment for advanced prostate cancer was for decades androgen deprivation by bilateral orchiectomy and/or oestrogen therapy. The limitations of these therapeutic modalities led to the development of GnRH agonists, which have made medical castration the preferred option among many patients with metastatic disease [Filicori 1994]. The efficacy and safety of these agents is now well established, and GnRH agonists are not associated with an increased risk of cardiovascular disease.

The therapeutic activity of the GnRH agonists is through pituitary down-regulation of their own receptors achieved by continuous and chronic administration, providing almost complete suppression of LH and FSH secretion leading to suppression of testicular function.

Achievement of castration levels of testosterone is generally obtained around one month after start of therapy. Of note, long term endocrine status and evolution of advanced prostate cancer treated with GnRH agonists are similar to those observed after surgical castration [Parmar 1987, DeSy 1988, Botto 1987] but in contrast to surgical castration, treatment with GnRH agonists initially results in a markedly, albeit temporary (~2 weeks), increase of gonadal androgen

release (flare-up phenomenon). The initial rise in testosterone may cause a temporary worsening of symptoms including increase in bone pain within the first days of treatment; for these reasons, GnRH agonists are contraindicated for use in patients presenting metastases with neurologic symptomatology, or other possible life-threatening metastases. The most significant side effects - hot flushes, decreased libido and erectile dysfunction - are linked to the pharmacological effect (castrate levels of testosterone) and are usually relatively mild and reversible upon cessation of therapy.

Since the discovery and synthesis of GnRH, many analogues of the native decapeptide have been synthesised in attempts to develop agonists with increased in vivo half-life and potency.

As shown in the amino acid sequences below, the major structural difference between the native decapeptide and the triptorelin agonist is the substitution of a different D-amino acid at position six, which is the hinge between the two active portions of the peptide. However, triptorelin retains the parts of the native decapeptide responsible for its biological activity.

Decapeptide	1	2	3	4	5	6	7	8	9	10
	Glu	-His	-Trp	-Ser	-Tyr	-Gly	-Leu	-Arg	-Pro	-Gly-NH ₂
Triptorelin	(pyro)	Glu	-His	-Trp	-Ser	-Tyr	-D-Trp	-Leu	-Arg	-Pro-Gly-NH ₂

GnRH has a L-glycine at position six, whereas triptorelin has a D-tryptophan. The substitution of the D-amino acid increases resistance to cleavage by proteolytic enzymes and increases biological potency relative to the native decapeptide [Barron 1982]. Triptorelin, like other GnRH agonists, has a short half-life in vivo ($t^{1/2}=5$ h), therefore, sustained-release dosage forms have been developed by combining the peptide with a biocompatible and biodegradable copolymer (lactide-glycolide). By modifying the molar ratio of lactic acid to glycolic acid, the peptide is released continuously over periods ranging from 28 days (1-month formulation) to 168 days (6-month formulation) following administration of a single intramuscular (i.m.) injection.

The 6-month triptorelin formulation (22.5 mg) has been evaluated in a multicentre, non-comparative phase III study in participants with advanced prostate cancer, conducted between July 2006 and August 2007 [Lundstrom 2009]. The results from the study have shown that the new triptorelin 6-month formulation (22.5 mg) rapidly induces and maintains castration in participants with locally advanced or metastatic prostate cancer. In the intention-to-treat (ITT) population, 97.5% (117/120) of participants were castrated (testosterone level <50 ng/dL) on Day 29, and 93.0% (107/115) of participants maintained castration from Week 8 (Day 57) to end of Week 48. The efficacy results of the 6-month formulation have been reviewed with those obtained in previous studies with the marketed triptorelin 1- and 3-month formulations. Results show that the rate of castration achieved with the 6-month formulation on Day 29, after the first triptorelin injection, was comparable to those with the 1-month and 3-month formulations [Breul 2017].

In terms of local tolerance at the injection site, intramuscular triptorelin injections were well tolerated and in the phase III study where injection site reactions were assessed by active questioning: 6.7% participants with injection-site reactions reported as adverse events (AEs), which is lower than for other 6-month GnRH formulations [Lundstrom 2009]. In a pooled analysis, very few (<5%) local adverse reactions at the injection site have been reported in clinical studies with all triptorelin sustained-release formulations (1-, 3- and 6-month) [Breul 2017].

A more detailed description of the product, including further details on administration procedures and dosage are provided in Section 6.

2.3 Benefit/Risk Assessment

Detailed information about the known and expected benefits and risks and reasonably expected AEs of triptorelin may be found in the IB.

2.3.1 Risk Assessment

A risk assessment for this study is provided in Table 3.

Table 3 Study Risk Assessment

Potential Risk of Clinical Significance	Summary of Data/Rationale for Risk	Mitigation Strategy
Study Intervention: Triptorelin		

There is no major known nonclinical risk associated with the study intervention
 
Clinical risks associated with the study intervention may include:
 
 • hot flushes • erectile dysfunction • loss of libido • impaired physical activities • metabolic syndrome • cardiovascular events • anxiety/depression • decreased bone mineral density • risk of abortion or foetal abnormality [a] 
See Section 8.3
	See IB Section 6.6.1	
Participant selection: Participants with significant medical conditions and at high risk of presenting treatment related SAEs and high-grade toxicity will be excluded from the study.
 
Participant monitoring: During the study, there will be close monitoring of the participants for safety including local tolerability (see Section 8.3.6)
 
Withdrawal criteria: Participants who become at risk of unacceptable toxicity will be withdrawn from the study intervention.

Study Procedures		
There are no specific risks related to the study design or procedures.	All procedures requested for the study are commonly used in clinical practice and the design does not create any specific risk or delay possible therapeutic option for participants	Not applicable

IB=investigator's brochure; SAE=serious adverse event

a Pregnancy is not relevant in this study population. However, reproductive risks are listed for completeness for female partners of participants who may become pregnant.

2.3.2 Benefit Assessment

Based on the nonclinical and clinical data generated up to finalisation of the protocol, treatment with triptorelin 6-month formulation may maintain castrate levels of testosterone for a longer period, i.e. 6 months (24 weeks), thereby reducing the need for frequent injections, in Chinese participants with locally advanced or metastatic prostate cancer to a similar extent as in a previous global phase III study.

2.3.3 Overall Benefit: Risk Conclusion

Taking into account the measures taken to minimise risk to participants, the potential risks identified in association with triptorelin are justified by the anticipated benefits that may be afforded to Chinese participants with locally advanced or metastatic prostate cancer.

3 OBJECTIVES AND ENDPOINTS

Table 4 Objectives and Endpoints

Objectives	Endpoints
Primary	

 To evaluate the efficacy of triptorelin pamoate 22.5 mg 6-month formulation in achieving castrate levels of testosterone To evaluate the efficacy of triptorelin pamoate 22.5 mg 6-month formulation in maintaining the castrate levels of serum testosterone 	
 Percentage of participants achieving castrate levels of serum testosterone (<50 ng/dL or 1.735 nmol/L) on Day 29 Percentage of participants maintaining the castrate levels from Week 8 to Week 24
Secondary	

 To assess the safety profile including local tolerability of triptorelin pamoate 22.5 mg 6-month formulation 	
 Incidence of TEAEs (including local tolerability) throughout the study i.e., up to Week 24 Change from baseline in clinical safety laboratory parameters (blood chemistry and haematology) at Week 24 Change from baseline in physical examination at Day 1, Week 12 and Week 24 Change from baseline in ECG at Week 4 and Week 24 Change from baseline in vital signs (blood pressure and heart rate) at each visit up to Week 24

 To demonstrate the effect of triptorelin pamoate 22.5 mg 6-month formulation on PSA response 	
 Percent change in PSA from baseline (prior to injection) at Week 12 and Week 24 (percent change in PSA is defined as the absolute value of difference between the PSA values at Week 12 and Week 24 and the baseline value divided by the baseline value)

 To assess the PK of triptorelin pamoate 22.5 mg 6-month formulation in a subset of 12 participants 	
 PK parameters for dosing interval up to 24 weeks: 
 t_{max} C_{max} AUC_{0-169} AUC_{last}

 To assess the PD of testosterone in a subset of 12 participants 	
 PD parameters for dosing interval up to 24 weeks: 
 t_{max} C_{max} t_{cast}

 To assess the PK of triptorelin pamoate 22.5 mg 6-month formulation for all participants 	
 Sparse plasma concentrations of triptorelin at pre-dose and post-dose at Weeks 4, 8, 12, 16, 20 and 24

 To assess the PD of testosterone for all participants 	
 Sparse serum concentrations of testosterone at pre-dose and post-dose at Weeks 4, 8, 12, 16, 20 and 24
Exploratory	

 To evaluate the PK/PD relationship between the PK of triptorelin pamoate 22.5 mg 6-month formulation and testosterone concentration versus time profiles (PD) 	

AUC_{0-169} =area under the plasma concentration time curve from time 0 to the visit on Day 169; AUC_{last} =area under the plasma concentration time curve from time 0 to the last quantifiable concentration; C_{max} =maximum concentration;

ECG=electrocardiogram; PD=pharmacodynamics; PK=pharmacokinetics; PSA=prostate specific antigen; t_{castr} =time to castration; TEAE=treatment-emergent adverse event; t_{max} =time to peak serum/plasma concentration

Note: A list of laboratory parameters to be assessed during the study are presented in Appendix 10.2.

4 STUDY DESIGN

4.1 Overall Design

This is a prospective, interventional, multicentre, open-label phase IIIb, single-arm study with a treatment period of 24 weeks for each participant. A total of 195 Chinese adult participants with locally advanced or metastatic prostate cancer will be enrolled in the study. All enrolled participants will receive one i.m. injection of the 6-month formulation containing 22.5 mg triptorelin pamoate on Day 1.

This study will consist of a 4-week screening period, during which participants with advanced or metastatic prostate cancer will be screened for eligibility. On Day 1, eligible participants will receive a single open-label administration of the study intervention. Following treatment on Day 1, visits will occur on Day 2, Day 3, Day 5, Day 8, Day 15, Day 22 in a subset of 12 participants, and for all participants on Day 29, Day 57, Day 85, Day 113, Day 141 and Day 169. For more details on sampling schedule see the SoA ([Table 1](#) and [Table 2](#)).

The maximum duration of the study is approximately 30 months from screening to the last study visit. Participants who complete all scheduled visits will be considered to have completed the study. Participants who complete the study will have final procedures and assessments performed at the final visit (Day 169). Participants who withdraw from the study before the completion of the Day 169 evaluation period will have early discontinuation procedures and assessments performed at their final visit.

The study design is illustrated in [Figure 1](#).

4.2 Scientific Rationale for Study Design

This single-arm, phase III study will investigate the efficacy, safety and PK/PD of triptorelin 6-month formulation in Chinese adult males with locally advanced or metastatic prostate cancer.

According to data from China National Cancer Registration Institute, prostate cancer has become the most common tumour in male urinary malignancies since 2008. The incidence rate was approximately 9.80/100,000 in 2014 and ranks the sixth common malignancy in male malignant tumours. The mortality of prostate cancer is 4.22/100,000, and it is the 9th common cause of death in all male malignancies. The staging varies widely between China and Western developed countries. In China, only 30% of newly diagnosed patients are clinically localised, and the rest are locally advanced or extensively metastatic disease, who have lost the chance of radical treatment with poor prognosis [[National Health Commission China 2019](#)]. This study will enrol adult Chinese men with advanced prostate cancer.

The non-comparative, open-label clinical study design is acceptable as the efficacy of triptorelin will be assessed by the percentage of participants achieving castrate levels of serum testosterone (defined as <50 ng/dL or 1.735 nmol/L) on Day 29 and maintaining castrate levels of serum testosterone from Week 8 to Week 24 (co-primary endpoints). Studies conducted in Western countries have shown that the rate of castration achieved with the 6-month formulation on Day 29, after the first triptorelin injection, was comparable to those with the 1-month and 3-month formulations [[Breul 2017](#)]. No studies have evaluated the 6-month triptorelin formulation in Chinese men with locally advanced or metastatic prostate cancer, thus the outcomes of this study intend to fulfil an unmet need and provide treatment convivence for the patient and physician.

This study will evaluate the PK/PD profile of triptorelin 6-month formulation in this study population. The blood sample collection scheme was designed to collect the minimum number of blood samples to help provide useful PK/PD information of study treatment in Chinese men with locally advanced or metastatic prostate cancer.

4.3 Justification for Dose

For this intervention, the term “dose” refers to the i.m. injection of triptorelin 22.5 mg created to guarantee the release of a monthly dose of 3.75 mg over a 169-day period. In addition, results from a phase III study have shown the 6-month triptorelin 22.5 mg formulation to induce and maintain castration in participants with locally advanced or metastatic prostate cancer, as well as demonstrate a good safety profile [Lundstrom 2009].

4.4 End of Study Definition

The end of the study (EoS) is defined as the date of the last visit of the last participant in the study as shown in the SoA ([Table 1](#) and [Table 2](#)).

The overall duration of the study (from first participant in, to last participant out) will be approximately 30 months. The study will be considered to have ended after the last participant has completed the last visit (at Week 24) in the study.

A participant is considered to have completed the study if they have completed all phases of the study including the last visit.

Criteria for study intervention discontinuation and participant discontinuation/withdrawal from the study are described in Section [7.1](#) and Section [7.2](#), respectively. Loss to follow-up is described in Section [7.3](#).

5 STUDY POPULATION

Prospective approval of protocol deviations to recruitment and enrolment criteria, also known as protocol waivers or exemptions, is not permitted.

5.1 Inclusion Criteria

Participants are eligible to be included in the study only if all of the following criteria apply:

1. Participant is capable of giving signed informed consent as described in Appendix 10.1 which includes compliance with the requirements and restrictions listed in the informed consent form (ICF) and in this protocol.
2. Participant must be over 18 years of age, at the time of signing the informed consent.
3. Has a histologically or cytologically confirmed adenocarcinoma, locally advanced or metastatic prostate cancer, which is staged T₃₋₄N_xM₀ or T_xN₁M₀ or T_xN_xM₁ according to the TNM classification (Appendix 10.4). Or participant has PSA recurrence after curative treatment and be a candidate for androgen deprivation therapy (ADT).
(Note: PSA recurrence after radical prostatectomy: PSA ≥ 0.2 ng/mL and rising, confirmed on a repeat test; PSA recurrence after radiation therapy: PSA increased 2 ng/mL than the lowest level.)
4. Has serum testosterone level >150 ng/dL (> 5.2 nmol/L).
5. Has expected survival time ≥ 12 months according to the investigator's assessment.
6. Has Eastern Cooperative Oncology Group (ECOG) performance status score ≤ 1 (see Appendix 10.5).
7. Has absence of another malignancy, other than local dermatological, for the previous 5 years.
8. Participant is male.
9. Male participants must agree that, if their partner is at risk of becoming pregnant, they will use an effective method of contraception. The participant must agree to use the contraception during the whole period of the study and for 9 months after the last dose of study intervention.

5.2 Exclusion Criteria

Participants are excluded from the study if any of the following criteria apply:

Medical conditions

1. Risk of a serious complication in the case of tumour flare (known or suspicion of vertebral metastases threatening spinal cord compression or significant obstructive uropathy).
2. Presence of another neoplastic lesion or brain metastases.
- 3a. Previous history of QT prolongation or concomitant use of medicinal products known to prolong the QT interval or with a known risk of torsades de pointes.
- 4a. Metastatic hormone-sensitive prostate cancer with high tumour burden.
(Note: high tumour burden: presence of visceral metastases and/or at least four bone lesions with at least one lesion outside the vertebral column and/or pelvis per CHAARTED study (Kyriakopoulos 2018).)

5. Metastatic castration-resistant prostate cancer.

Prior/concomitant therapy

6. Previous surgical castration.

- 7a. Previous hormone therapy (including abiraterone) for prostate cancer within 6 months prior to study screening.
- 8a. Previous cytotoxic chemotherapy treatment within 6 months prior to study screening.
- 9a. Use of finasteride or dutasteride within 2 months prior to study screening.
10. Previous hypophysectomy or adrenalectomy.
- 11a. Any current use or use within 6 months prior to treatment start of medications which are known to affect the metabolism and/or secretion of androgenic hormones: ketoconazole, aminoglutethimide, oestrogens and antiandrogens.
Note: antiandrogen: enzalutamide, apalutamide or darolutamide is allowed (if required per investigator's clinical judgement) due to no interference on the metabolism and/or secretion of androgenic hormones.
- 12a. Current use of systemic or inhaled corticosteroids (topical application permitted).
13. Any previous use of traditional Chinese medicine or herbal products within 1 month prior to study screening or planned use during the study of products, which are known to have cytotoxic effect or affect the metabolism and/or secretion of androgenic hormones.

Prior/concurrent clinical study experience

- 14a. Participation in another study with an investigational drug or treatment within 3 months prior to study screening or within 5 drug half-lives of the investigational drug (whichever is the longer).

Diagnostic assessments

15. Severe kidney or liver impairment (creatinine >2 x upper limit of normal (ULN), aspartate aminotransferase (AST) and alanine aminotransferase (ALT) >3 x ULN).

Other exclusions

16. Any concomitant disorder or resulting therapy that is likely to interfere with participant compliance, the i.m. administration of the drug or with the study in the opinion of the investigator.
17. Known hypersensitivity to triptorelin or any of its excipients, GnRH, other GnRH agonist/analogue.
18. Known active use of recreational drug or alcohol dependence in the opinion of the investigator.

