6.8 Concomitant Therapy

Any medication (excluding prior disease-specific medications) or vaccine (including over the counter prescription medicines, recreational drugs, vitamins, and/or herbal supplements) that the participant had received within 2 months before triptorelin administration or receives during the study must be recorded on the eCRF along with:

- Generic or trade name
- Reason for use
- Dates of administration including start and end dates
- Dosage information including dose, frequency and route of administration

The medical monitor should be contacted if there are any questions regarding concomitant or prior therapy.

The following concomitant medications are not permitted during this study:

- Any treatment or procedure with a specific or potential effect on androgenic hormones be administered concomitantly to the study drug (will be considered as a protocol violation). Per investigator's clinical judgement, suggest offering short-term administration of an older generation androgen receptor antagonist to M1 participants starting study intervention to reduce the risk of the 'flare-up' phenomenon.
- Any medication which raises prolactin levels and those affecting pituitary secretion of gonadotropins
- All drugs mentioned as prohibited in the exclusion criteria:
 - Finasteride or dutasteride.
 - Medications which are known to affect the metabolism and/or secretion of androgenic hormones: ketoconazole, aminoglutethimide, oestrogens.
 - Systemic or inhaled corticosteroids (topical application permitted).
 - Cytotoxic chemotherapy, abiraterone.
 - Any traditional Chinese medicine or herbal products previous used within 1 month prior to study start or plan to be used during the study, which are known to have cytotoxic effect or affect the metabolism and/or secretion of androgenic hormones.
 - Concomitant use of medications known to prolong QT interval should not be given (class IA (e.g. quinidine, disopyramide) or class III (e.g. amiodarone, sotalol, dofetilide, ibutilide) antiarrhythmic medicinal products, methadone, moxifloxacin, antipsychotics).

The following concomitant medications are permitted during this study, but they must be monitored closely, and every effort should be made to keep their dose and dose regimen constant throughout the course of the study:

- Analgesics: are allowed when necessary for pain relief.
- Anticonvulsants (e.g phenobarbital): long-term therapy may have additional risk for osteoporosis.

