9.4.6 Subgroups Analyses

No subgroups analysis will be performed.

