5.7.1.3 Statistical/analytical issues

Adjustments for Covariates

This is a single-arm study, and no statistical comparisons will be performed, so covariates adjustment is not required.

Interim Analyses and Data Monitoring

Please refer to section 3.

Multicentre Studies

This is a multicentre study conducted in China.

Multiple Comparisons/Multiplicity

No multiple testing will be performed in this study because this is a single-arm descriptive safety and efficacy study.

Active-Control Studies Intended to Show Equivalence (if applicable)

Not applicable.

5.7.2 *Analysis of Primary Efficacy Endpoint*

5.7.2.1 *Endpoint, Treatment Effect and Estimand Definition*

The co-primary endpoints of efficacy are

- To determine the percentage of participants achieving castrate levels of serum testosterone (<50 ng/dL or 1.735 nmol/L) on Day 29 ± 3 days (Week 4) and
- To determine the percentage of participants maintaining the castrate levels of serum testosterone (<50 ng/dL or 1.735 nmol/L) from Week 8 (Day 57 ± 3 days) to Week 24 (Day 169 ± 3 days).

Percentage of participants achieving castrate levels of serum testosterone on Day 29

The percentage of participants achieving castrate levels of serum testosterone on Day 29 will be obtained as the number of participants achieving castrate levels on Day 29, divided by the number of participants in the FAS. The formula is

$$\text{Percentage} = \frac{\text{Number of participants achieving castrate levels on Day 29}}{\text{Number of participants in the analysis set}} \times 100$$

Percentage of participants maintaining castrate levels from Week 8 to Week 24

Percentage of participants maintaining castrate levels of serum testosterone from Week 8 to Week 24 for the FAS will be calculated as the number of participants achieving castrate levels of serum testosterone at all visits from Week 8 to Week 24, divided by the number of assessable participants in the analysis set. The formula is

$$\text{Percentage} = \frac{\text{Number of participants maintaining castrate levels from Week 8 to Week 24}}{\text{Number of assessable participants in the analysis set}} \times 100$$

To derive the percentage of participants maintaining castration levels of testosterone, missing data between Week 8 and Week 24 will be handled as follows:

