5.7.3 Analysis of Key Secondary Efficacy Endpoints

5.7.3.1 Endpoint, Treatment Effect and Estimand Definition

The secondary efficacy variable is the percent change in PSA from baseline (prior to injection) measured at Week 12 and Week 24. Percent change in PSA is defined as the value of difference between the PSA values at Week 12 and Week 24 and the baseline value divided by the baseline value.

$$\text{Percent change from baseline (\%)} = \left(\frac{\text{PSA value at Week 12 or Week 24} - \text{Baseline value}}{\text{Baseline value}} \right) \times 100$$

5.7.3.2 *Main Secondary Analysis*

PSA percent change from Baseline will be reported at each subsequent visit, using descriptive statistics on the FAS and PPS.

Observed value will also be summarized for the FAS. Descriptive statistics to be presented include number of available observations (n), mean, median, SD, minimum, maximum, standard error mean (SEM, calculated as SD divided by the square root of n), coefficient of variation (CV) and 95% CI for mean.

Individual PSA level data versus visit will be plotted by participant on a semi-logarithmic scale on the FAS. The arithmetic mean (\pm SD) PSA levels versus visit will also be provided.

All PSA data will be listed by participant and timepoint on all participants enrolled.

5.7.3.3 *Subgroup Analysis*

No subgroup analyses will be performed.

5.7.4 *Analysis of Other Secondary Efficacy Endpoints*

Not applicable.

5.7.5 *Analysis of Exploratory Endpoints*

An exploratory endpoint is defined in Protocol, but the analysis details will be described in a separate data analysis plan.

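### Every PSA summary pools men with and without permitted androgen receptor inhibitors, so the pooled fall may overstate triptorelin's contribution

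*Protocol*

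**What the plan says.** The PSA objective in Protocol section 3, repeated in SAP 2.1, is an attribution statement: "To demonstrate the effect of triptorelin pamoate 22.5 mg 6-month formulation on PSA response". The endpoint is percent change from baseline at Weeks 12 and 24, in a single arm.

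Criterion 11a in Protocol 5.2 excludes antiandrogens, but its note says that "enzalutamide, apalutamide or darolutamide is allowed" if the investigator judges it necessary, "due to no interference on the metabolism and/or secretion of androgenic hormones". The note sets no limit on the number of users and none on when the drug may start. Protocol 6.8 adds a second route to androgen receptor blockade. At the investigator's judgement, it says to "suggest offering short-term administration of an older generation androgen receptor antagonist to M1 participants" against flare.

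On the analysis side, SAP 5.7.3.2 states that "PSA percent change from Baseline will be reported at each subsequent visit, using descriptive statistics on the FAS and PPS". It adds observed values, individual and mean plots, and a listing by participant and timepoint. SAP 5.7.3.3 states: "No subgroup analyses will be performed". Protocol 9.4.6 agrees: "No subgroups analysis will be performed". SAP 5.7.1.3 reasons that "no statistical comparisons will be performed, so covariates adjustment is not required". Concomitant medications for the study indication are tabulated by ATC class and preferred name on the Safety Set (SAP 5.5), but that table is not linked to PSA.

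**The concern.** The reason given for allowing the three drugs protects the testosterone endpoints. It says nothing about PSA. The protocol's own summary of changes describes them as androgen receptor inhibitors, and Protocol 2.2 gives androgens a major role in the growth of prostatic tissue. A drug that blocks the receptor can therefore be expected to lower PSA without changing serum testosterone. With no control arm, any such fall would be counted as triptorelin's in the planned tables. A reader of the study report could not tell from those tables how much of the fall came from men on triptorelin alone.

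**Working it through.** **Do the planned outputs separate users?**

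- FAS (SAP section 4): defined by testosterone measurements and treatment failure. Concomitant drugs play no part, so users stay in.
- PPS (SAP section 4): removes FAS members with major deviations that could affect the primary endpoint, which is testosterone. Use permitted under 11a is not on its face such a deviation. The deviation specification that decides this is not among the documents.
- PSA tables and plots (SAP 5.7.3.2): one group, with no split by medication. The listing names no medication flag.
- Medication tables (SAP 5.5): count users on the Safety Set, without PSA.

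So no planned PSA output makes the separation.

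**Design figure.** The documents contain no computed figure for PSA. The only one is for the co-primary endpoints, and it reproduces. With n = 165 and a null of 85%, the smallest count with upper-tail probability at most 0.025 is 150. Power is 88.32% at 93% (stated 88.3%), and 165/0.85 = 194.1, rounded up to 195. This point changes none of it.

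**How far could pooling shift the PSA result?** Let u be the share of users, m the mean fall without an inhibitor and c the mean fall with one.

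Pooled fall = u·c + (1 − u)·m, so shift = u·(c − m).

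The documents give none of u, m or c; all values below are assumptions. For m = 85 and c = 98 at u = 0.10: 0.10 × 98 + 0.90 × 85 = 9.8 + 76.5 = 86.3, a shift of 1.3 points.

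| Assumed m, c | 10% users | 30% users | 50% users | Shift in points |
|---|---|---|---|---|
| 85%, 98% | 86.3% | 88.9% | 91.5% | 1.3 / 3.9 / 6.5 |
| 85%, 95% | 86.0% | 88.0% | 90.0% | 1.0 / 3.0 / 5.0 |
| 80%, 98% | 81.8% | 85.4% | 89.0% | 1.8 / 5.4 / 9.0 |
| 60%, 95% | 63.5% | 70.5% | 77.5% | 3.5 / 10.5 / 17.5 |

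The user share that moves the mean by one point is 1/(c − m). That is 1/13 = 7.7% for the first row and 1/35 = 2.9% for the last. Among the 165 evaluable men in the design, these are about 13 men and 5 men.

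**The case against.** PSA here is a descriptive secondary endpoint; no hypothesis is tested and the primary analyses are untouched. Use may be rare. The note applies only where the investigator judges the drug necessary. High-burden metastatic hormone-sensitive disease and metastatic castration-resistant disease are excluded (4a, 5). The note entered only with Version 4.0, dated 08 March 2024, and the documents do not say how many men were enrolled under it. The SAP already tabulates and lists the medications and lists PSA by participant, so the two could be matched, and SAP section 1 allows further exploratory analyses. Declining subgroup analyses was a deliberate choice. A split table also has its own bias. If inhibitors go to men with worse disease or a poorer PSA course, the remaining men may make triptorelin look better than it is.

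Most of this stands and limits the weight of the point. It does not remove it. SAP section 1 requires analyses not identified in the SAP to be labelled as such, so later matching would carry less weight than a planned table. The selection problem is a reason to show the split beside the pooled result, not in place of it.

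A reader might infer that the PSA objective cannot be answered at all. The documents do not support that. Usage is unknown, and in each scenario above most of the pooled fall is already present without an inhibitor. Nor do they state how strongly these drugs act on PSA.

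**Conclusion.** The gap is real and modest. The plan aims to demonstrate triptorelin's effect on PSA, allows drugs that can plausibly lower PSA by another route, and pools their users in every PSA summary. If use is more than trivial, the pooled fall mixes the two effects and may overstate triptorelin's contribution. With assumed falls of 85% and 98%, the overstatement is 1.3 to 6.5 points at 10% to 50% use. Across the wider assumed range it runs from 1.0 to 17.5 points.

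Three assumptions carry this. The drugs lower PSA further when added to triptorelin; the documents do not say so. Use starts after the baseline sample; a man already on the drug would have a lowered baseline, and his percent fall could err the other way. And the deviation specification does not remove permitted users from the PPS.

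It would be wrong to extend the point to the testosterone co-primary endpoints, the power or the sample size, all of which are unaffected.

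**What to change.** In SAP 5.7.3.2, prespecify one descriptive table of PSA percent change at Weeks 12 and 24, by use of an androgen receptor antagonist or inhibitor up to that visit, beside the pooled FAS result. Use three groups and give the number of men in each:

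- none;
- short-term older-generation antagonist only;
- enzalutamide, apalutamide or darolutamide.

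Note in SAP 5.7.3.3 that this is the one exception to the rule against subgroups, and make the matching change in Protocol 9.4.6. Word the PSA conclusion so that attribution to triptorelin goes no further than this table supports.

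The cost is one table and smaller numbers per group; drug names and start and end dates are already recorded under Protocol 6.8. The groups are formed by treatment given after baseline at the investigator's discretion. The table is therefore supportive and does not isolate triptorelin's effect.

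Separately, reconcile the passages on antiandrogens. Criterion 11a excludes them apart from the three named drugs. Section 6.8 bars treatments that act or may act on androgenic hormones and, in the same item, suggests an older-generation antagonist for M1 participants. The documents should make clear which use counts as permitted, so that the groups and the PPS can be applied consistently.
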